3.1.1. Endpoints

Primary Endpoints:

- 1) Total volume of voids over a 6-hour period
- 2) Total natriuresis over a 6-hour period

Secondary endpoints:

- 1) Volume of voids between 0-2 hours, 2-4 hours and 4-6 hours post initiation of treatment.
- 2) Heart Failure Symptom Scoring/Symptom Improvement- (Kansas City Cardiomyopathy questionnaire)
- 3) Overall Satisfaction with Treatment- (Treatment Satisfaction Survey)

3.1.2. Safety Endpoints

- 1) Patient reported Pain
- 2) Increases in serum creatinine of 0.5 mg/dL or greater
- 3) Local skin reactions including hematoma, induration, infection, thrombosis, necrosis etc.
- 4) Occurrence of treatment-emergent Adverse Events (AEs) or Serious Adverse Events (SAEs)

4. SELECTION OF STUDY POPULATION

4.1. Inclusion Criteria

Female and male subjects are eligible for inclusion only if all of the following criteria are met:

Inclusion Criteria (low risk, intermediate risk):

- An Institutional Review Board (IRB) approved informed consent is signed and dated prior to any study-related activities
- Male and female subjects ≥ 18 years of age
- History of at least 3 months treated heart failure (NYHA class II/III/IV), or recent hospitalization for heart failure; presenting to HFBC with decompensated heart failure symptoms including elevated jugular venous pressure, dyspnea and peripheral edema where the decision is made to give IV diuretics
- Able to participate in the study in the opinion of the investigator
- Has the ability to understand the requirements of the study and is willing to comply with all study procedures

4.2. Exclusion Criteria

A Subject is not eligible for inclusion if any of the following criteria apply

- Presenting with symptoms where it is anticipated that there is a high chance of hospitalization such as ischemia, uncontrolled arrhythmia, infection, hemodynamic instability (elevated or low blood pressure), respiratory compromise, or electrolyte abnormalities (>25% increase in creatinine from baseline, potassium, hyponatremia)
- On experimental medication or currently participating in a cardiovascular research study.
- Presence or need for urinary catheterization, urinary tract abnormality or disorder interfering with urination
- Any surgical or medical condition which in the opinion of the investigator may interfere with participation in the study or which may affect the outcome of the study
- Inability to comply with study requirements

4.3. Enrollment

It is anticipated that enrollment of 40 participants will take approximately 3 to 4 months based on HFBC current estimate of providing IV diuretics 15 times a month.

4.4. Removal of Subjects from Therapy/Premature Discontinuation

Participants may discontinue participation at any time without penalty or loss of benefits to which the subject is otherwise entitled.

The subject's participation may be terminated by the investigator for safety reasons or if, in the opinion of the investigator, continued participation may interfere with clinical management.

The study will be stopped early if there is a significant difference in number of patients with intolerable side effects: Ototoxicity, severe discomfort, burning and stinging at the access site, itching, and/or pain.

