| ENDPOINTS | Primary Endpoints: |
| | Total volume of voids over a 6-hour period Total natriuresis over a 6-hour period |
| | Secondary endpoints: |
| | Volume of voids between 0-2 hours, 2-4 hours and 4-6 hours post initiation of treatment. Heart Failure Symptom Scoring/Symptom Improvement- (Kansas City Cardiomyopathy questionnaire) Overall Satisfaction with Treatment- (Treatment Satisfaction |
| | Survey) |
| | Safety endpoints: |
| | Patient reported Pain Increases in serum creatinine of 0.5 mg/dL or greater Local skin reactions including hematoma, induration, infection, thrombosis, necrosis etc. Occurrence of treatment-emergent Adverse Events (AEs) or Serious Adverse Events (SAEs) |
| STATISTICAL ANALYSIS | Determination of Sample Size: For this pilot study, the determination of sample size was primarily based on clinical consideration; with the aim to yield meaningful preliminary data. |
| | Statistical Analysis Plan: A full statistical analysis plan will be developed. All data will be analyzed as intention-to-treat. Continuous variables will be presented as mean \pm standard deviation and will be compared using the Students t -test (2-tailed), unpaired. Differences between treatment groups for the categorical variables will be analyzed using the chi-square test. For the purposes of this study, P values \leq .05 will be considered significant. |
| | Early Stopping Rules: The study will be stopped early if there is a significant difference in number of patients with intolerable side effects: Ototoxicity, severe discomfort, burning and stinging at the access site, itching, and/or pain. |

| Time and Events Table | Screening Phase | Pre-Dose | Start of Dosing | Dosing | 6 hours post Start of Dosing |
|---|--------------------|----------|--------------------|--------|---------------------------------|
| Informed Consent | Х | | | | |
| Confirmation of Eligibility | Х | | | | |
| Co-morbidity | Х | | | | |
| Cardio-Pulmonary Examination | Х | | | | |
| Serum Creatinine | Х | | | | Х |
| Weight and Height | Х | | | | |
| Vital Signs | Х | Х | Х | Х | Х |
| 12-lead EKG | Х | | | | |
| Collection and Measurement of Urine Voids | | | Х | Х | Х |
| Urine Sodium | | Х | | | Х |
| Clinical Chemistry | Х | | | | Х |
| BNP/NT ProBNP | | Х | | | Х |
| Study Drug Administration | | | Х | | Х |
| Injection Site Pain Assessment | | | | | Х |
| Injection Site Inspection | | Х | | | Х |

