7.4. Assessment of Relatedness to Study Drug

The Investigator will assess each AE and SAE for causality based on their medical judgment and the observed symptoms associated with the event. Each AE and SAE will be assessed as related or unrelated to study drug based on the following criteria:

- Unrelated This category applies to those AEs that the Investigator determines are most likely due to extraneous causes (disease, environment, etc.)
- Related This category applies to those AEs that the Investigator determines are most likely due to test drug.

7.5. Method, Frequency, and Time Period for Detecting Adverse Events and Serious Adverse Events

Patients will be evaluated for AEs and SAEs at the end of the 6 hour observation. After the subject has had an opportunity to spontaneously mention any problems, the Investigator should inquire about AEs by asking a non-leading question such as "How are you feeling?"

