7.6.3. Clinical Laboratory Abnormalities and Other Abnormal Assessments as AEs and SAEs

The Investigator should exercise his or her medical and scientific judgment in deciding whether an abnormal laboratory finding or other abnormal assessment is clinically significant.

Abnormal laboratory findings (e.g., clinical chemistry, hematology, and urinalysis) or other abnormal assessments (e.g., ECGs, vital signs) that are judged by the Investigator as clinically significant must be recorded as AEs or SAEs if they meet the definition of an adverse event. Clinically significant abnormal laboratory findings or other abnormal assessments that are detected after study drug administration or that are present before study drug administration but worsen after study drug administration should be assessed for AE criteria.

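### The only study-level stopping rule concerns ototoxicity and discomfort-type symptoms, and sets no pause for deaths or other SAEs

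*Combined protocol and SAP*

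**What the plan says.** The rule appears in section 4.4: "The study will be stopped early if there is a significant difference in number of patients with intolerable side effects: Ototoxicity, severe discomfort, burning and" (the list continues with access-site stinging, itching and pain). The synopsis, under Early Stopping Rules, has the same list: "intolerable side effects: Ototoxicity, severe discomfort, burning and stinging at the access site, itching, and/or pain". No other section describes a halt, a hold, a safety board or a review step for the study as a whole.

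Section 3.1.2 lists safety endpoints that go beyond that list:
- for the kidney: "Increases in serum creatinine of 0.5 mg/dL or greater"
- for the injection site: "Local skin reactions including hematoma, induration, infection, thrombosis, necrosis etc"
- for events in general: "Occurrence of treatment-emergent Adverse Events (AEs) or Serious Adverse Events (SAEs"

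The other safety provisions work case by case. In 4.4 a subject's "participation may be terminated by the investigator for safety reasons". Section 7.6.1 requires notice of a death or life-threatening event within 24 hours, whatever the cause, and full information on other SAEs within 24 hours. Section 7.6.5 adds reporting to the IRB and FDA. Section 8.3 summarizes safety data descriptively.

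On causality, the introduction to 7.4 asks for a rating against study drug, but the Related category reads: "This category applies to those AEs that the Investigator determines are most likely due to test drug".

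**The concern.** The sponsor decided that a pilot of this size needs a stopping rule, then confined it to tolerability. The gravest outcomes in the protocol's own endpoint list, death and other SAEs, have no stated consequence for further enrolment. SCP-101 is investigational. The earlier experience that the protocol reports for it is a ten-patient crossover in stable heart failure, whereas this trial enrols patients with decompensated disease. If a patient dies after dosing, the protocol says whom to tell and how fast, but not whether the next patient may be randomized meanwhile.

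The 7.4 wording is a second, smaller gap. Section 3.1 lists both products under Study Drug and labels SCP-101 the test treatment; 5.2.1 also uses the term study test drug for SCP-101. Read literally, an event after IV furosemide cannot be rated related, so the two arms could not be compared on related events.

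**Working it through.** **1. Text check.** Each outcome against what the protocol does about it:

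| Outcome | Where collected | Individual or reporting action | Study-level pause |
|---|---|---|---|
| Intolerable ototoxicity, discomfort, burning and stinging, itching, pain | 3.1, 6.1.8 | Subject may be withdrawn (4.4) | Yes, on a significant difference (4.4, synopsis) |
| Death or life-threatening SAE | 3.1.2, 7.2 | Notice within 24 hours (7.6.1); IRB and FDA (7.6.5) | None stated |
| Other SAE | 3.1.2, 7.2 | Full report within 24 hours (7.6.1); IRB and FDA (7.6.5) | None stated |
| Infection, thrombosis, necrosis at the site | 3.1.2, 6.1.9 | Severity and causality rated (6.1.9) | Only through intolerable pain or discomfort |
| Creatinine rise of 0.5 mg/dL or more | 3.1.2, 6.1.2 | An AE only if "judged by the Investigator as clinically significant must be recorded as AEs or SAEs if they meet the definition of an adverse event" (7.6.3) | None stated |

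The plan gives no figure on this point to reproduce.

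**2. Would adding SAEs to the present rule be enough?** The rule names no test and no schedule of looks. Assume the chi-square test and P ≤ .05 of section 8.2, applied once at the full 20 v 20. For k events against 0:

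- Uncorrected: χ² = 40k/(40 − k). k = 3 gives 120/37 = 3.24, p = 0.072; k = 4 gives 160/36 = 4.44, p = 0.035.
- Continuity-corrected: χ² = 40(k − 1)²/[k(40 − k)]. k = 5 gives 640/175 = 3.66, p = 0.056; k = 6 gives 1000/204 = 4.90, p = 0.027.
- Fisher exact, two-sided: k = 4 gives p = 0.106; k = 5 gives p = 0.047.

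So 4, 5 or 6 events against none would be needed, depending on the test. Equal counts in the arms give p = 1.0 and never trigger. A significance test suits common symptoms, not rare grave events, so a pause for those should not rest on one.

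**3. How often would a pause after the first such event occur?** The documents give no rate. With an assumed per-patient rate p of death or life-threatening SAE in the reporting window, the chance of at least one in 40 patients is 1 − (1 − p)^40:

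- p = 0.1%: 1 − 0.999^40 = 4%
- p = 0.5%: 1 − 0.995^40 = 18%
- p = 1%: 1 − 0.99^40 = 33%

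**4. Would a count-based pause for the other events be clearly right?** Pool both arms and count patients with a related SAE, a serious local reaction or a creatinine rise of 0.5 mg/dL or more. With X ~ Binomial(40, p) and p again assumed:

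| Assumed rate | P(X ≥ 2) | P(X ≥ 3) |
|---|---|---|
| 1% | 6% | 1% |
| 2% | 19% | 5% |
| 5% | 60% | 32% |
| 10% | 92% | 78% |

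The answer depends almost wholly on a background rate that the documents do not supply.

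**The case against.** The strongest reply is that silence in one rule is not inaction. The rule says when the study will stop; it does not say that nothing else can stop it. Deaths reach the sponsor within 24 hours whatever their cause, the IRB and FDA also receive SAE reports, and 9.1.1 binds conduct to federal regulations whose content cannot be judged from here. The sponsor is the clinic itself and the trial is open label, so those who would decide see events directly. A reader might infer that no number of deaths could stop the trial. The documents do not support that: it is true of this one rule only.

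Second, severe discomfort might be read widely, because 7.3 uses that phrase to define a severe AE. The synopsis and 3.1 tie discomfort to the access site, which favours the narrow reading. Even the wide reading still needs a significant between-arm difference and does not cover a death or other SAE as such.

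Third, the stakes are limited: one dose, one visit, six hours of observation, and patients likely to be hospitalized are excluded. That stands, and it keeps the severity low.

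Fourth, 8.2 promises a full statistical analysis plan, which may hold more. That cannot be checked, but 8.2 mentions no stopping criteria, and a rule that halts enrolment belongs beside the existing one in the IRB-approved protocol.

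**Conclusion.** The gap is real but small. The only study-level rule requires a significant difference in intolerable ototoxicity or discomfort-type symptoms, and the protocol itself triggers no pause for deaths or other SAEs. Outside bodies could act on the reports they receive; what is missing is a stated consequence inside the protocol. This conclusion rests on the text and on no event rate. The 7.4 wording is a related defect that is just as easily cured.

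A reader might go further and ask for a mandatory count-based pause covering other related SAEs, serious local reactions and creatinine rises. The documents do not support making that a requirement. At an assumed 5% rate such a pause would occur with probability 60% (count of 2) or 32% (count of 3), creatinine rises after usual-care IV furosemide would contribute, and nothing in the plan says which count is right. It is a trade-off for the sponsor. Nor are creatinine rises lost: they are measured at 6 hours and are a named endpoint. Only their status as AEs depends on judgment.

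Label: cheap improvement, low severity.

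**What to change.** 1. In 4.4 and the synopsis, keep the present rule and add: enrolment pauses after any death or life-threatening SAE in either arm, regardless of causality, and resumes only after the investigator has reviewed all events to date and the IRB has agreed.
2. In 7.4, replace *test drug* in the Related category with *study drug (SCP-101 or IV furosemide)*, in line with 3.1.
3. Optional, at the sponsor's choice: a pause after a pre-set number of patients with another related SAE, a serious local reaction, or a creatinine rise of 0.5 mg/dL or more. If adopted, fix the number before the first patient and state the background rate assumed.

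Items 1 and 2 cost one IRB amendment with three short edits. The trigger uses reports already due within 24 hours, so no new committee, procedure or patient is needed. The downside is an occasional short pause, in a planned 3 to 4 month enrolment, for an event later judged unrelated, plus investigator and IRB time. One limit remains: section 7 assesses AEs only through discharge, so a later death may not reach the trigger.

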5. TREATMENTS

5.1. Treatments Administered

Study drug will be administered by qualified study staff only in accordance with the procedures described in this protocol.

5.2. Identity of Investigational Product(s)

Furosemide Injection Solution, 8mg/mL (SCP-101): 80 mg undiluted buffered furosemide solution, manufactured by Cook Pharmica, Bloomington, IN, USA for scPharmaceuticals, Inc. under GMP conditions (test treatment).

Contains Tris Hydrochloride, Sodium Chloride and may contain Sodium Hydroxide and Hydrochloric acid for pH adjustment: pH 7.4 (7.0 - 7.8). Furosemide Injection Solution (SCP-101) will be provided by scPharmaceuticals to the investigational site.

Furosemide Injection, USP: Furosemide Injection, Solution, single dose determined by Investigator (maximum dose 160mg) by intravenous bolus administration. (reference treatment)

5.2.1. Labeling

Study test drug (Furosemide Injection Solution (SCP-101)) will bear a label that meets applicable laws for an investigational drug, which may include, but is not limited to, the following information:

- Federal law statement
- Batch number
- Storage information

Furosemide Injection, USP for intravenous administration will be obtained from local pharmacy commercial stock with commercial labeling.

5.2.2. Storage and Handling

Store at 20° - 25°C, (68° - 77°F), excursions permitted between 15°C and 30°C, (between 59°F and 86°F). Protect from Light.

5.3. Method of Assigning Subjects to Treatment Groups

5.3.1. Treatment Assignment/Randomization

Randomization will be performed in blocks of 4. Treatment assignment will be performed by means of numbered envelopes, which will identify the treatment group.

5.4. Selection of Doses in the Study

The attending physician will decide the IV furosemide dose to be administered (max 160mg). IV furosemide is to be administered by single IV bolus over approximately 2 minutes.

The subcutaneous furosemide dose is predefined at 80 mg total – 30 mg of which is administered over the first hour followed by 12.5 mg/hour for 4 hours.

5.5. Procedures for Blinding

Not Applicable - This is an open label study.

5.6. Prior and Concomitant Therapy

Heart failure patients are generally on multiple medications used in the management of heart failure. Additionally the majority of patients are on prescription or over-the-counter medications for one or more co-morbidities. The clinic staff will evaluate these medications on a case by case basis and decide what medications may be used on the day of administration. This determination will be made prior to randomization.

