The company has previously conducted a Phase I pilot study (NCT02350725) to investigate the pharmacodynamics and pharmacokinetic parameters of Furosemide Injection Solution (SCP-101) administered subcutaneously as compared to oral furosemide. The study was a randomized open-label cross-over study in patients with stable HF. Patients were mildly symptomatic with NT-proBNP of >300 pg/mL. Treatments were separated by a 14 +/- 3 day interval. Subcutaneous administration of Furosemide Injection Solution (SCP-101) (8mg/mL; 80 mg total), was delivered using a B Braun Perfusor® Space Infusion Pump System as 30 mg over the first hour followed by 12.5 mg per hour over the subsequent 4 hours. Reference treatment consisted of 80mg p.o. furosemide.

Ten subjects were enrolled (80% males) with a mean age of 69.9 years and mean plasma NTproBNP of 1638 ng/mL. All patients were on standard medication including ACE inhibitors and beta blockers. Main daily dose of oral furosemide was 40 mg/day.

Subcutaneous administration of the novel formulation was well-tolerated. All participants achieved therapeutic plasma furosemide levels of over 1000ng/mL within one hour of start of subcutaneous infusion. Therapeutic plasma levels were maintained for a minimum of 5 hours (Figure 1).

Figure 1: Mean Plasma Furosemide Levels after SC or Oral Administration

Figure 1. Plasma furosemide levels were measured just prior to dosing (Time 0) and at 30, 60, 120, 240, 300, 360 and 480 minutes post dosing. Mean plasma levels + 2 SE across the 10 subjects are shown for each treatment period.

Plasma furosemide levels in the plateau phase (60-300 minutes post start of infusion) were maintained in a narrow range (67%-93%) from the Cmax when compared to oral (11% - 40%). P.o. furosemide administration resulted in highly variable plasma levels: 90% of the participants achieved levels of 1000ng/mL at some point following administration; but only one participant (10%) maintained plasma levels over 1000 ng/mL for 5 hours. The mean total furosemide exposure (expressed by area under the curve, AUC) was 66% higher after subcutaneous administration when compared to oral (p < 0.0001).

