5.8. Treatment Compliance

All study medication will be administered by study personnel and all information regarding study drug administration will be documented.

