6. STUDY PROCEDURES

6.1. Study Measurements and Assessments

6.1.1. Assessment of Efficacy

Diuresis:

Urine will be collected from start of treatment through 6 hours post initiation of treatment. Individual voids will be measured and then pooled over the 6 hour time period, and the volume of the pool will be recorded. Time of voids and volume of each void will be recorded.

Natriuresis:

Participants will not be given any fluid by mouth during the 6-hour observation period, except when required for taking oral medication, in which case fluid intake will be limited to 100mL over the 6 hour period.

A 5mL aliquot of the first void, and a 5 mL aliquot of the total 6 hour pool will be obtained by the study staff for determination of sodium.

Symptomatic Improvement

Symptom scoring using the Kansas City Cardiomyopathy questionnaire will be performed prior to drug administration and at the end of the 6 hour observation period. A treatment satisfaction survey will be conducted at 6 hours.

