6.1.10. Meals and Dietary Restrictions

Participants will not be given any fluid by mouth during the 6-hour observation period, except when required for taking oral medication, in which case fluid intake will be limited to 100mL over the 6 hour observation period.

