Appendix 1: Time and Events Schedule

| Time and Events Table | Screening Phase | Pre-Dose | Start of Dosing | Dosing | 6 hours post Start of Dosing |
|---|--------------------|----------|--------------------|--------|---------------------------------|
| Informed Consent | Х | | | | |
| Confirmation of Eligibility | Х | | | | |
| Co-morbidity | Х | | | | |
| Cardio-Pulmonary Examination | Х | | | | |
| Serum Creatinine | Х | | | | Х |
| Weight and Height | Х | | | | |
| Vital Signs | Х | Х | Х | Х | Х |
| 12-lead EKG | Х | | | | |
| Collection and Measurement of Urine Voids | | | Х | Х | Х |
| Urine Sodium | | Х | | | Х |
| Clinical Chemistry | Х | | | | Х |
| BNP/NT ProBNP | | Х | | | Х |
| Study Drug Administration | | | Х | | Х |
| Injection Site Pain Assessment | | | | | Х |
| Injection Site Inspection | | Х | | | Х |
| Randomization to Treatment Sequence | Х | | | | |
| Kansas City Cardiomyopathy questionnaire | | Х | | | Х |
| Treatment Satisfaction Survey | | | | | Х |
| Treatment Emergent Serious Adverse Events | | | X | X | Х |

Verbally indicate the number on the Numeric Rating Scale that best represents the intensity of pain at or around the injection site NOW, with 0 being no pain and 10 being the worst possible pain.

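### Same-day home diuretics are neither standardised nor listed for collection, so an unmeasured effect can enter both primary endpoints, adding variance and possible chance imbalance of unknown direction

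*Combined protocol and SAP*

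**What the plan says.** Section 5.6 leaves study-day medication to clinic staff, who "decide what medications may be used on the day of administration" patient by patient. It then adds: "This determination will be made prior to randomization". It does not name diuretics and sets no common rule for them.

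Sections 6.1.1 and 6.1.10 withhold fluid during the 6-hour observation, "except when required for taking oral medication, in which case fluid intake will be limited to 100mL over the 6 hour period" (wording of 6.1.1). Oral dosing inside the collection window is therefore possible.

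On recording, section 5.8 commits only to this: "all information regarding study drug administration will be documented". Table 1 in the synopsis and "Appendix 1: Time and Events Schedule" have rows for co-morbidity and study drug administration. Neither has a row for prior or concomitant medication, or for the last diuretic dose and its time.

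The first primary endpoint in section 3.1.1 is "Total volume of voids over a 6-hour period"; the second is total sodium excretion over the same window. Section 8.2 compares continuous variables by an unpaired two-sided t-test with no covariate.

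**The concern.** A home diuretic acts on exactly what the primary endpoints measure. Patients enter with treated heart failure or a recent heart failure admission, so many are likely to be on one. That is an inference, because section 5.6 does not say so. A dose taken that morning or during collection would add urine and sodium that are credited to the randomized route.

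Little in the plan would separate the two sources. No urine volume is measured before dosing. The first sodium sample is the first void after treatment starts in section 6.1.3, although the schedule marks it as pre-dose, so there is no clear sodium baseline either. Randomization is in blocks of 4 with no stratification.

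At stake are the precision of the two primary comparisons and the ability to check whether a difference, or the lack of one, reflects unequal background diuretic use.

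**Working it through.** The plan states no power, effect size or margin (section 8.1 bases the sample size on clinical consideration), so there is no figure to reproduce.

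**Inputs from the documents**
- 20 patients per arm (section 3.1).
- Urine output 1460 mL, SD 730 mL, in this clinic's usual care with visits averaging 220 minutes (section 1).
- In the Phase I pilot, furosemide AUC "was 66% higher after subcutaneous administration when compared to oral", with 80 mg by each route (section 1.1).
- Home oral furosemide 40 mg/day in those pilot patients (section 1.1). No figure is given for this clinic's patients.

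**Assumptions:** exposure proportional to dose; share of patients taking a same-day diuretic q = 25% to 75%; volume added per taker c = 200 to 400 mL, with 1000 mL as an extreme.

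**1. Exposure.** 80 mg oral relative to 80 mg subcutaneous: 1/1.66 = 0.60. Half of that for 40 mg oral: 0.30. This is an upper figure for a dose taken before time zero, since part will have cleared.

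**2. Standard error without carry-over.** 730 × √(2/20) = 231 mL. At 80% power and two-sided 0.05, the t-test detects about 664 mL.

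**3. Effect on the mean difference.** If the share of takers is the same in both arms and the effect is additive, each arm's mean rises by q × c and the difference is unchanged. A simulation with q = 50% and c = 500 mL gave 662 mL against a true 663 mL.

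**4. Effect on variance.** SD′ = √(730² + q(1−q)c²).

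| q | c (mL) | SD′ (mL) | Power at 664 mL |
|---|---|---|---|
| none | 0 | 730 | 80% |
| 25% or 75% | 200 | 735 | 79% |
| 50% | 400 | 757 | 77% |
| 50% | 1000 | 885 | 64% |

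**5. Chance imbalance.** The SD of the difference in number of takers between arms is √(2 × 20 × q(1−q)): 2.7 at q = 25% and 3.2 at q = 50%. A difference of 4 patients is therefore unremarkable. It shifts the arm difference by (4/20) × 200 to 400 = 40 to 80 mL. That is 0.05 to 0.11 of the SD (40/730, 80/730), or 17% to 35% of the standard error (40/231, 80/231). It can go either way.

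Natriuresis could not be worked through, because the documents give no SD for sodium.

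**The case against.** A reader might infer that background diuresis pulls the two routes together and so favours the hypothesis that subcutaneous furosemide is an effective alternative. The documents do not support this. Staff decide before randomization, so what they permit cannot depend on the arm, and an additive effect cancels from the difference in means that the t-test uses. Only the ratio of the arms and the standardized effect shrink. A true pull toward zero needs a ceiling or an interaction that the documents do not describe. Added noise does make a non-significant result somewhat more likely, and that should not be read as similarity.

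A reader might also infer that home diuretic use could never be identified afterwards. That goes too far. The CRF is not shown, staff review each patient's medications under section 5.6, and section 9.1.5 keeps clinic notes as source documents. What can be said is that the protocol does not list the drug, dose or time for collection, so exact clock times may not be recoverable.

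Two further objections limit the size:
- Section 1 says oral diuretics would likely be ineffective in stable patients with volume overload, and the exposure ratio comes from stable, mildly symptomatic patients. It is a ratio of plasma AUC, not of urine or sodium.
- The 730 mL SD comes from usual care in this clinic and may already include home diuretic use. Adding the variance again could count it twice.

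Finally, the exception "except when required for taking oral medication" is a fluid limit. It neither expects nor mentions diuretic dosing, and section 5.6 equally lets staff withhold a drug.

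All of this stands. It removes the direction and reduces the size, but not the gap in what the plan lists for collection.

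**Conclusion.** The point holds as one about unmeasured variation. Same-day home diuretic use is left to case-by-case judgement, may extend into the collection window and is not listed for collection, while both primary endpoints count everything passed from 0 to 6 hours. The expected consequence is added variance and possible chance imbalance, with unknown direction.

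The size is probably modest. With 200 to 400 mL per taker, power at 664 mL falls from 80% to between 77% and 79%, and an imbalance of 4 patients moves the difference by 40 to 80 mL. The fall to 64% needs 1000 mL per taker in half the patients. All these figures rest on an assumed share of takers, an assumed effect per taker and an SD from shorter visits.

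This does not invalidate a 40-patient pilot. It is worth correcting because it costs little and the information may be hard to recover later.

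**What to change.** Without changing which medications staff allow:

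1. Add a CRF item and a schedule row, completed before randomization, for the name, dose and clock time of each diuretic taken in the previous 24 hours, and for any diuretic staff will permit during collection. The schedule marks randomization in the Screening column, so the row belongs there and not under Pre-Dose.
2. In the SAP still to be written, pre-specify an analysis of both primary endpoints adjusted for same-day diuretic status (yes/no), defined only from that pre-randomization record, beside the unadjusted t-test.
3. Record actual diuretic intake from 0 to 6 hours and report it by arm, descriptively only. In an open-label trial this intake comes after randomization and may depend on the arm, so it should not serve as an adjustment covariate or define a subgroup.

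The cost is one CRF item with its schedule row, a short intake record during collection, and one degree of freedom in the adjusted analysis.
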